1.2.1.1. Inclusion criteria

Each patient must meet the following criteria:

- Provide written informed consent by the patient prior to any study-related procedure
- Men aged ≥ 18 years
- Histo-pathologically confirmed adenocarcinoma of the prostate
- Radical Prostatectomy with curative intent performed no more than 8 weeks before randomisation
- High-risk criteria of disease progression, defined as follows:
 - Gleason score ≥ 8 on prostatectomy specimen, and/or
 - Pre-RP PSA level ≥ 20 ng/mL, and/or
 - Primary tumour stage 3a (pT3a) (with any PSA and any Gleason score)
- Post-RP PSA levels ≤ 0.2 ng/mL at 6 weeks.
- Eastern cooperative oncology group (ECOG)/world health organisation (WHO) performance status of 0 to 1

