1.3.2.2. Safety assessments

- AE(s) and SAE(s) according to the NCI-CTCAE version 4.0 scale
- Clinical laboratory tests (haematology (full blood count including red blood cells (RBC), haemoglobin, haematocrit, mean cell volume (MCV), mean cell haemoglobin (MCH), mean cell haemoglobin concentration (MCHC), white blood cells (WBC) with differential and platelet count; neutrophils, lymphocytes, monocytes, eosinophils, basophils) and biochemistry (urea, creatinine, total bilirubin, chloride, bicarbonate, sodium, potassium, calcium, inorganic phosphate, alkaline phosphatase (ALP), aspartate aminotransferase (AST), alanine aminotransferase (ALT), gamma-glutamyl transferase (GGT), albumin, total protein, total cholesterol, triglycerides, and fasting glucose)).
- Concomitant medications/therapies and non-drug therapies.
- Concomitant and surgical procedures
- Death reports

- Physical examination and vital signs (height, weight, heart rate and sitting blood pressure (systolic and diastolic).

1.3.2.3. *Other assessments*

The other assessments will be the following:

- Demography and characteristics at screening:
 - Country,
 - Race (Asian; Black/African American; Caucasian/White; Native Hawaiian/Other Pacific Islander, American Indian/Alaska Native, Multiple),
 - Date of visit,
 - Date of birth.
- Prostate Cancer History (prior to RP)
 - Date of first histological diagnosis
 - Gleason Score (Primary Pattern, Secondary Pattern, Total Score),
 - cTNM Staging (T, N, M) and method used (MRI, CT Scan, X-Ray, Transrectal Ultrasound, Clinical Judgment, Other),
 - Last available PSA level (ng/mL),
 - Last available testosterone level (ng/dL).
- Radical Prostatectomy Procedure
 - Date of surgery
 - Pelvic lymphadenectomy (Yes; No),
 - If yes, extended / not extended,
 - Gleason Score (Primary Pattern, Secondary Pattern, Total Score),
 - pTNM Staging (T, N, M).
- WHO/ECOG Performance Status Scale.
- Significant Medical or Surgical history (including ongoing medical history other than prostate cancer related).
- Prior and concomitant medications/therapies and non-drug therapies.

1.3.2.4. *Withdrawal / discontinuation from the study*

The date of early withdrawal and the primary reason for early withdrawal will be recorded (adverse event, protocol violation, consent withdrawn, lost-to follow-up, other).

1.3.2.5. *Compliance*

Compliance assessments will be the following:

- Injection triptorelin administration performed (Yes/No),

- Date of drug administration,

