3.2.1.3. *Exploratory efficacy analysis*

To identify prognostic factors among Gleason score on prostatectomy specimen ($\leq 6 / = 7 / \geq 8$, with ≤ 6 considered as the reference), country, Pre-RP PSA level ($<20 / \geq 20$ ng/mL), primary tumour stage (T1 / T2 / T3 / T4 with T3 considered as the reference) and age (<65 years / ≥ 65 years) are associated with BRFS outcome, Cox proportional hazard regression models will be used. Each parameter will be analysed in an univariate model where the hypothesis of proportional risks will be checked graphically. Significant parameters at a 20%-level will be retained for the multivariate Cox model. Associations between significant parameters will be tested in order to keep only non correlated variables in the multivariate model. The association between two categorical or binary variables will be tested using Chi-square or Fisher's exact test. Associations will be considered as statistically significant if $p < 0.01$. A backward selection method will be used to identify the final set of prognostic factors (exit p-value set to be 0.05). Treatment will then be added to this final model to assess the effect of treatment when adjusted for these factors.

The syntax with SAS using the PHREG procedure will be:

```
CCI [REDACTED]
```

CCI [REDACTED]

3.2.2. *Safety*

Safety analysis will be analysed on safety population according to the actual treatment approach followed.

3.2.2.1. *Adverse events*

Adverse events will be graded by the investigator according to the NCI CTCAE version 4.0.

AEs will be coded according to the Medical Dictionary for Regulatory Activities (MedDRA; version 16.0) and will be classified by PT and SOC.

Listings will be presented for all patients (description, time to onset, duration, seriousness, grade, relationship to study drug, action taken and outcome) and sorted by treatment group, patient id, start time of AEs, primary system organ class, preferred term and verbatim text for all adverse events recorded during the study.

Listings of serious adverse events (SAE), adverse events leading to study withdrawal, leading to study drug discontinuation, drug related adverse events, adverse events with NCI CTC Grade > 2 and listings of deaths will also be presented.

Treatment Emergent Adverse Events (TEAE) will be flagged (*) in the adverse events listing and will be summarised.

For the triptorelin treatment group, a TEAE is defined as any AE that occurs during the active phase of the study if:

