Discontinued patients will be listed and a summary table of the number and percentage of patients who withdrew from the study and the reasons for withdrawal will be presented overall and by treatment group.

3.2.6. *Demographic and baseline characteristics*

Descriptive summary statistics will be provided by treatment group and overall on the ITT population and on the safety population if there is at least 10 % difference between the safety and the ITT population, for demographic and baseline characteristics. It includes assessments as detailed in the Section 1.3.2.3 ('Demography and characteristics at baseline', 'Prostate cancer history', 'Radical prostatectomy procedure' and 'WHO/ECOG Performance Status Scale'). To assess homogeneity of treatment groups at baseline, 95% CI of proportion for qualitative variable or 95% CI of mean for quantitative variable will be provided.

In addition the proportion of patients with a Gleason score ≥ 8 on prostatectomy specimen and with a Pre-RP PSA level ≥ 20 ng/mL; with a Gleason score ≥ 8 on prostatectomy specimen and with a primary tumour stage 3a; with a Pre-RP PSA level ≥ 20 ng/mL and with a primary tumour stage 3a; with a Gleason score ≥ 8 on prostatectomy specimen and with a Pre-RP PSA level ≥ 20 ng/mL and with a primary tumour stage 3a will be tabulated.

3.2.7. *Medical and surgical history*

Descriptive summary statistics will be provided by treatment group and overall on the ITT population for ‘Significant Medical or Surgical History’.

A frequency table of the number and percentage of patients will be provided for medical history by SOC and PT.

3.2.8. *Compliance*

Descriptive summary statistics will be provided by treatment group and overall on the ITT population, for current prostate cancer therapy. It includes assessments as detailed in the Section 1.3.2.5 ‘Compliance’ and the time between first drug administration and RP (days) and the time between each drug intake (days). .

If the drug intake occurs outside the allowed time-window (time between each drug intake should be between 84 and 99 days ($3*30.4375 \pm 7$ days)), the date of dose intake and the number of days since the last drug intake will be listed.

3.2.9. *Prior and concomitant medications and non-drug therapies*

Descriptive summary statistics will be provided by treatment group and overall on the safety population for ‘Prior and concomitant medications and non-drug therapies’.

Prior and concomitant medications:

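### The exploratory prognostic Cox models reduce age and pre-RP PSA to two classes and do not separate pT3a within T3; finer coding would cost only wording

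*SAP*

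**What the plan says.** Section 3.2.1.3 of the SAP lists five candidate factors: Gleason score, country, pre-RP PSA, primary tumour stage and age.

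- **Age** has two levels: "and age (<65 years / ≥ 65 years) are associated with BRFS outcome".
- **Pre-RP PSA** has two levels, cut at 20 ng/mL.
- **Stage** has four levels, listed just before age: "primary tumour stage (T1 / T2 / T3 / T4 with T3 considered as the reference) and age (<65 years". There is no class for 3a.

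Each factor is tested alone and kept if significant at 20%. Correlated factors are removed after chi-square or Fisher tests at 1%. Backward selection then uses a 5% exit, and treatment is added to the final model.

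Other sections define or collect the same variables more finely:

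- The entry criteria in 1.2.1.1 are joined by and/or. They include "Pre-RP PSA level ≥ 20 ng/mL, and/or" and "Primary tumour stage 3a (pT3a) (with any PSA and any Gleason score").
- Section 1.3.2.3 records "Last available PSA level (ng/mL"), date of birth, and both clinical and pathological TNM. Section 3.2.10 derives age in years.
- Section 3.2.6 tabulates stage 3a at baseline, for example patients "with a Gleason score ≥ 8 on prostatectomy specimen and with a primary tumour stage 3a".

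**The concern.** The section's purpose is to find prognostic factors, and its procedure drops any factor that misses a p-value limit. Coding that weakens a factor makes a true one more likely to be dropped. A PSA of 21 and one of 100 count as the same, while 19 and 21 count as different.

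The stage coding raises a separate issue. The trial defines risk by pT3a, but the model has a single T3 class and uses it as the reference. Because of the and/or rule, a T3 tumour other than pT3a can enter through Gleason score or PSA, so the reference class may be mixed. Both clinical and pathological T are collected and 3.2.1.3 names neither, so two programmers could build different variables from the same sentence.

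What is at stake is the list of prognostic factors and the supplementary treatment estimate adjusted for them. The trial's main result is not at stake.

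**Working it through.** **Inputs from the SAP (1.3.4).** 61 relapses, 226 patients (113 per arm), relapse probability at 36 months of 40% versus 20%, two-sided 5% test, 90% power.

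**Reproducing the plan's event count.** HR = ln(0.80)/ln(0.60) = 0.437. Schoenfeld's formula gives 4 × (1.960 + 1.282)² / (ln 0.437)² = 61.3 events, and 61 events give 89.9% power. The stated 61 reproduces.

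**Which event count applies here.** Section 3.2.1.3 does not say whether it uses the first 61 events or all of them. Under the plan's own rates, 36 months for everyone gives 113 × 0.40 + 113 × 0.20 = 67.8 relapses without dropout, and about 63 with 5% annual dropout. So 61 is a fair working figure, slightly low.

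**Assumptions the SAP does not supply.** The distribution of age and PSA, the shape of their effect, and its size. I take a normal factor with a linear log-hazard effect and HR 1.4 per SD, then vary these.

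**Formulas.** With share p below cut c (in SD units), the information kept is E = φ(c)² / [p(1 − p)]. With D events, univariate power is about Φ(ln(HR) × √(D × E) − z), where z = 1.960 for the 5% test and 1.282 for the 20% screen.

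Example for a median split: E = 0.3989² / 0.25 = 0.637. Then 0.3365 × √(61 × 0.637) = 2.097. Power is Φ(2.097 − 1.960) = 55%, and the chance of passing the screen is Φ(2.097 − 1.282) = 79%.

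| Coding | E | Equivalent events | ln(HR) × √(D × E) | Power at 5% | Passes 20% screen |
|---|---|---|---|---|---|
| Continuous | 1 | 61 | 2.628 | 75% | 91% |
| Median split | 0.637 | 39 | 2.097 | 55% | 79% |
| 70/30 split | 0.576 | 35 | 1.994 | 51% | 76% |
| 80/20 split | 0.490 | 30 | 1.839 | 45% | 71% |

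The chance of losing a true factor at the screen therefore rises from 9% to 21–29%.

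**Varying the effect size (continuous versus median split, 5% test).** HR 1.3: 54% versus 37%. HR 1.5: 89% versus 71%.

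**Varying the distribution and shape.**

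- Normal factor: the loss is smallest at the median, 1 − 2/π = 36%. It is 42% at 70/30 and 51% at 80/20.
- Age cut at 65, assumed mean 62–70 and SD 5–8 years: 36% to 56%.
- Uniform factor: 25% at the median. Strongly bimodal factor: about 10%. True threshold at the cut: none.
- Right-skewed factor with a linear effect on the raw scale, cut between the 30th and 90th percentile: 43% to 77% (lognormal, log SD 0.8) or 35% to 70% (exponential).

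The power formula is a first-order approximation. For uneven splits the result also depends on whether the smaller group has the higher or lower hazard.

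**Stage.** No arithmetic applies, because the SAP does not give the share of T3 patients who are not pT3a. The point rests on comparing 1.2.1.1, 1.3.2.3 and 3.2.6, which distinguish pT3a or pathological T, with 3.2.1.3, which does neither.

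**The case against.** The other side has five good arguments.

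- **The loss is conditional.** A reader might infer that the coding discards over a third of the information as a fact. The SAP gives neither the distributions nor the shape of effect, and the loss is nil if risk really steps at the cut. The figure holds only under the stated assumptions.
- **The PSA cut has a reason.** 20 ng/mL is itself an entry criterion, and asking whether an entry criterion is prognostic is coherent. Only the stage coding can blur an entry criterion.
- **Levels T1 and T4 do not contradict the design.** A reader might think they do, since the trial recruits on pT3a. But that is one of three alternative criteria, and nothing in 1.2.1.2 excludes other T stages as such. What remains is the possible mixture inside T3 and the unnamed source of T.
- **The power figures are not those of the planned procedure.** HR 1.4 per SD has no source in the SAP, the event count may exceed 61, and the formula is univariate while the 5% exit applies in a multivariable model. The figures illustrate the size of the effect on detection.
- **The effect on treatment inference is small.** Treatment is randomised, so coarse coding of prognostic factors does not confound it. The primary Cox model in 3.2.1.1 uses treatment, country, centre and Gleason score, and none of these three factors.

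The cut-points are also fixed in advance, so there is no bias from choosing them on the data. Even so, the finer data are already collected and the present coding makes true factors harder to find.

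**Conclusion.** The point holds as a cheap improvement to an exploratory analysis. The coding is as described, and the SAP collects or derives what is needed to refine it.

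Under a normal distribution and a linear log-hazard effect, each binary split loses at least 36% of that factor's information. With 61 events and HR 1.4 per SD, this means power of roughly 45–55% instead of 75%, and a 71–79% instead of 91% chance of passing the screen. Flatter distributions lose less and a true threshold at the cut loses nothing. Skewed factors with a linear raw-scale effect can lose more.

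The stage point is a matter of definition: T is unspecified and the T3 reference can be mixed. Its numerical effect cannot be estimated from the SAP.

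A reader might infer that the trial's treatment result is weakened or biased. The SAP does not support that: the log-rank test and the primary Cox model do not use these codings, and randomisation protects the comparison.

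**What to change.** In section 3.2.1.3:

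1. Enter age and log(pre-RP PSA) as continuous terms in the univariate and multivariate models, and check linearity on the log-hazard scale.
2. Keep the cuts at 65 years and 20 ng/mL for descriptive tables. The PSA cut is an entry criterion and remains useful there.
3. Code stage from the pathological T recorded at prostatectomy, as pT2 or lower, pT3a, and above pT3a.
4. In the association step, use a correlation, t-test or ANOVA where a continuous term is involved, and keep chi-square or Fisher for pairs of categorical factors.

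The cost is a few lines of SAP text, the linearity checks and a small programming change. No new data are needed, and the primary analysis does not change.

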RAP Final Version 3 [22-JUL-2019]

15/248

CCI

1 Adverse events (AEs) will only be collected until Visit 5/Month 9; this corresponds to three months after the last triptorelin injection for those patients in the triptorelin group. After this visit, only AEs and SAEs related to triptorelin according to Investigator's judgement should be reported (with the exception of AEs resulting in death that should be reported until the end of the study).

Patients will not be withdrawn from the study if study medication is discontinued. Follow-up will continue for all patients every 3 months and for at least 36 months.

1.3.4. *Planned sample size*

It is planned to recruit 226 patients in approximately 10 centres in two countries (China and Russia) according to the Sample Size Determination.

The sample size estimation was based on the primary efficacy endpoint of BRFS. Assuming that with RP alone, the probability of biochemical (PSA) relapse as defined in Section 4.2.1 of the study protocol at 36 months after RP is 40% in high-risk patients (Section 2.1 of the study protocol, Table 1), and anticipating that immediate adjuvant hormonal therapy added to RP will reduce this probability to 20% (percentage considered to be clinically relevant), 113 patients per treatment group (226 in total) are required in order to detect such a difference using a two-sided log-rank test at a significance level of 5% and a power of 90%, assuming a common 1% exponential dropout rate (corresponding to an approximate 5% dropout rate per year).

These 226 patients are required to observe 61 BR in order to achieve 90% power. For patients with no sign of disease progression at 36 months post-randomisation, monitoring will continue until the 61 BR events are observed at the study global level. If the 61 events are observed before all patients complete the 36 months post-randomisation monitoring period, the study will be continued until those patients reach their 36 month visit (Visit 14).

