- it occurred up to 12 months after the first injection,
and
- it was not present prior to receiving the first dose of study drug, or
- it was present prior to receiving the first dose of study drug but the intensity increased during the active phase of the study, or
- it was present prior to receiving the first dose of study drug, the intensity is the same but the drug relationship became related during the active phase of the study.

Summary tables of adverse events will be provided with the number and percentage of patients with adverse events classified by primary system organ class, preferred term (ordered alphabetically) and associated NCI/CTC worst grade. In the event of multiple occurrences of the same adverse events being reported by the same patient, the maximum intensity (Grade 5 > Grade 4 > Grade 3 > Grade 2 > Grade 1 > missing > not applicable) and the most serious causality (related) will be chosen.

A summary table of all adverse events will be presented by treatment arm up to visit 6. An overall summary table of all adverse events will be presented starting at visit 6.

For the first year (visit 6 excluded), summary tables of adverse events will be presented separately for each treatment arm:

- For the triptorelin treatment group, treatment emergent adverse events per decreasing frequency, treatment emergent serious adverse events, treatment emergent non serious adverse events, treatment emergent drug related adverse events, treatment emergent drug related serious adverse events, treatment emergent drug related non serious adverse events, treatment emergent adverse events leading to study withdrawal and treatment emergent adverse events leading to study drug discontinuation (drug withdrawn or drug interrupted).
- For the active surveillance group, adverse events per decreasing frequency, serious adverse events, non serious adverse events and adverse events leading to study withdrawal will be presented.

For AEs starting from visit 6, the summary tables of adverse events will be presented overall. The following summary tables will be presented: adverse events per decreasing frequency, serious adverse events, non serious adverse events and adverse events leading to study withdrawal.

3.2.2.2. *Laboratory data*

A separate listing of normal ranges for SI units will be provided by age where relevant.

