3.2.11. Visit windows

All data will be organised and analysed according to the scheduled visits outlined in the protocol. However, actual observation times may differ from the scheduled visit times and where this occurs the results should be allocated to the most appropriate visit. Therefore, time intervals (e.g. visit windows) have been constructed so that every observation collected after baseline visit can be allocated to a particular time point. If more than one record occurs within the same visit window where only one assessment is expected then the following rule should be applied (except for PSA and testosterone sample): for pre-study assessments only one record is expected and corresponds to the baseline visit; for post-treatment assessments the closest non-missing result to the scheduled visit should be used.

Scheduled visit	Time interval (days)
Baseline [V2]	1
Month 3 [V3]	2 to 138
Month 6 [V4]	139 to 229
Month 9 [V5] ^(a)	230 to 321
Month 12 [V6]	322 to 412
Month 15 [V7]	413 to 503
Month 18 [V8]	504 to 595
Month 21 [V9]	596 to 686
Month 24 [V10] ^(a)	687 to 777
Month 27 [V11]	778 to 868
Month 30 [V12]	869 to 960
Month 33 [V13]	961 to 1051
Month 36 [V14] ^(a)	1052 to 1142
X visit post Month 36 - Every 3 months	$((36+3*X-1.5)*30.4375+2)$ to $((36+3*X+1.5)*30.4375+1)$
Time interval (days): Date of visit – Date of baseline visit +1	
(a) sHRQoL assessment	

3.2.12. *Window for assessment for the PSA and testosterone parameters*

Testosterone (only in the triptorelin treatment group) should be assessed at 3; 6 and 9 months (± 14 days). At visit 3, evidence of lack of castration will be confirmed by a second test at least 2 weeks later.

PSA should be assessed every 3 month (± 14 days) except at Visit 2 (Baseline, Day 1 Month 0). Elevated PSA concentration (>0.2 ng/mL) must be confirmed by a second test 4 to 6 weeks later (acceptable delta of 14 days).

Scheduled visit	Time interval (days) for serum testosterone assessment		Time interval (days) for PSA Level assessment	
	As per protocol (± 14 days)	Used for analysis (Consecutive intervals)	As per protocol (± 14 days)	Used for analysis (Consecutive intervals)
Month 3 [V3] ^(a,b)	78 to 106	2 to 138	78 to 106	2 to 138
Month 6 [V4] ^(a,b)	170 to 198	139 to 229	170 to 198	139 to 229
Month 9 [V5] ^(a,b)	261 to 289	230 to 321	261 to 289	230 to 321
Month 12 [V6] ^(b)	--	--	352 to 380	322 to 412
Month 15 [V7] ^(b)	--	--	444 to 472	413 to 503
Month 18 [V8] ^(b)	--	--	535 to 563	504 to 595

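### By-arm AE tables run past the Month 9 end of full AE collection, and later AEs are pooled over arms: the cut-off and the late denominator need to be fixed

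*SAP*

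**What the plan says.** **Collection.** The AE footnote to the schedule in SAP Section 1.3.3 says "Adverse events (AEs) will only be collected until Visit 5/Month 9". It continues: "After this visit, only AEs and SAEs related to triptorelin", in the investigator's judgement, are to be reported, "with the exception of AEs resulting in death that should be reported until the end of the study".

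**Tabulation.** Section 3.2.2.1 uses a later boundary: "A summary table of all adverse events will be presented by treatment arm up to visit 6". The detailed summaries follow the same boundary: "For the first year (visit 6 excluded), summary tables of adverse events will be presented separately for each treatment arm". After that, the arms are combined: "For AEs starting from visit 6, the summary tables of adverse events will be presented overall". The late summaries listed are AEs by decreasing frequency, serious AEs, non-serious AEs and AEs leading to study withdrawal. None is restricted to drug-related AEs.

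**Treatment-emergent window.** For triptorelin, a treatment-emergent AE (TEAE) qualifies if "it occurred up to 12 months after the first injection" and it is new, has worsened or has become related.

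**Visit allocation.** Section 3.2.11 says "All data will be organised and analysed according to the scheduled visits outlined in the protocol" and gives day windows of 230 to 321 for Month 9 and 322 to 412 for Month 12 (Visit 6).

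**Analysis principle.** Sections 2.4 and 3.2.2 analyse safety by the treatment actually received.

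**The concern.** After Visit 5 the two arms report under different rules. A surveillance patient who has not been given triptorelin can then contribute only a fatal AE. A triptorelin patient can contribute any AE judged related, as well as a fatal one. A by-arm table of all AEs that runs beyond Visit 5 therefore ends with a stretch in which a difference between arms can come from the reporting rule alone.

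From Visit 6 the problem reverses. The events still reportable are almost all triptorelin-related or fatal, yet they are shown over a denominator that includes patients never given triptorelin. The first effect tilts against triptorelin and the second dilutes its late toxicity. They sit in different tables, so they cannot be assumed to cancel.

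Overall safety of immediate castration is a stated secondary objective (Section 1.1.2), and AE incidence regardless of relationship is a listed safety endpoint (Section 3.1.3).

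**Working it through.** **Inputs.** Month length 30.4375 days and the visit windows (Section 3.2.11); end of full collection at Visit 5/Month 9 (Section 1.3.3); 113 patients planned per arm, 226 in total (Section 1.2.1).

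**The plan's own windows.** The SAP's formula for visits after Month 36, applied to month M, runs from (M − 1.5) × 30.4375 + 2 to (M + 1.5) × 30.4375 + 1.
- M = 9: 230.3 to 320.6; stated 230 to 321.
- M = 12: 321.6 to 411.9; stated 322 to 412.

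Both are reproduced.

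**Length of the unequal stretch, by onset date.**
- Nominal Month 9: 9 × 30.4375 + 1 = 274.9, day 275.
- Nominal Month 12: 12 × 30.4375 + 1 = 366.25, day 366.
- Visit 6 excluded by the windows: 321 − 275 = 46 days = 1.5 months; 46/321 = 14% of the by-arm period.
- First year to Month 12: 366 − 275 = 91 days = 3.0 months; 91/366 = 25%.

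**If AEs are grouped by the visit at which they are reported.** AEs arising after Visit 5 are reported at Visit 6 and excluded from the by-arm tables. The gap is close to zero, but these events enter the pooled tables.

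**Effect per patient in the by-arm table.** Each triptorelin patient counted only because of a related AE in the gap adds 1/113 = 0.9 percentage points to that arm alone. The SAP gives no event counts. Assuming 1 to 5 such patients over 91 days, the addition is 0.9 to 4.4 points. At the same rate over 46 days (× 46/91) it is 0.4 to 2.2 points.

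**Dilution in the pooled tables.** With r patients having a related AE and no later triptorelin use on surveillance, the pooled percentage is r/226 against r/113 in triptorelin-treated patients: ratio 113/226 = 0.50. For an assumed r = 10, that is 4.4% against 8.8%. Three assumptions move the ratio:
- If s surveillance patients later receive triptorelin at the same risk, the ratio is (113 + s)/226: 0.55 for s = 11, 0.60 for s = 23 and 0.70 for s = 45. The last is 0.40 × 113, the relapse probability assumed for surgery alone in Section 1.3.4.
- For any AE, with r = 10, f further patients per arm with a fatal AE and s = 0, the ratio is (10 + 2f)/(2 × (10 + f)): 0.58 for f = 2 and 0.67 for f = 5.
- Unequal safety arms move it either way: 105/(105 + 113) = 0.48; 120/(120 + 106) = 0.53.

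**TEAE window against table cut-off.** Under the day windows, a triptorelin AE with onset on about days 322 to 366 is a TEAE by definition but falls outside the first-year TEAE tables, which exclude Visit 6.

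**The case against.** The by-arm gap depends on how AEs are assigned to a period. Section 3.2.11 organises all data by scheduled visit, and Section 3.2.2.1 excludes Visit 6 by name, so grouping by reporting visit is a possible reading. A reader might infer that 1.5 to 3 months of the by-arm tables are certainly not like-for-like. The text does not support that certainty. Section 3.2.2.1 speaks of AEs starting from Visit 6 and of events occurring within 12 months of the first injection, both of which favour onset date, but the SAP does not settle it. This objection stands as a limit on the claim. It does not clear the plan, because the other reading moves the same events into the pooled tables.

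A reader might also infer that the plan will report a late triptorelin-related incidence understated by up to half. It plans no such figure: the late tables cover all AEs and are labelled overall, so their percentages are correct as pooled percentages. Nor is one half a strict bound, as the unequal-arm figures show. What remains is that a pooled percentage made up mostly of related events does not describe the patients exposed.

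The surveillance tables carry no TEAE definition, but Section 2.8 treats pre-treatment AEs as baseline data, so this is not shown to be an error.

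The practical effect is limited. By the SAP's own exposure formula (Section 3.2.10), three injections given on schedule end exposure at about Month 9, a period with full collection in both arms. First-year drug-related TEAEs have triptorelin-only tables. Listings keep arm and relationship to drug (Section 3.2.2.1), deaths are compared by arm through overall and disease-specific survival (Sections 3.2.1.2.2 and 3.2.1.2.3), and withdrawals for AEs are tabulated by group (Section 3.2.4). The table shells are not available here and may fix cut-offs or footnotes; the text would still have to agree with them.

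**Conclusion.** The concern holds in a limited form. The collection rule and the table boundaries do not match.

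If AEs are grouped by onset date, the final 46 days (14%) or 91 days (25%) of the by-arm tables are not like-for-like and tilt against triptorelin. If grouped by reporting visit, that gap is close to zero and the events pass into the pooled tables.

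In those tables, related events show at about half the percentage found in triptorelin-treated patients. That factor rests on the planned 1:1 split, the full safety set as denominator, and no later triptorelin use on surveillance; later use makes the dilution smaller. All event and crossover counts used above are illustrative.

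The consequence is confined to descriptive safety tables. The information can be recovered from the listings, and no test or efficacy conclusion changes. It is worth correcting before the tables are produced.

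**What to change.** - End the by-arm comparison of all AEs at the patient's actual Visit 5 date (the nominal Month 9 day if that visit is missing), assigning AEs by onset date.
- Put AEs with later onset in separate tables by treatment received. Show triptorelin-related AEs over triptorelin-exposed patients, with surveillance patients who later receive triptorelin shown separately. Show fatal AEs by group to the end of the study.
- Footnote the change in collection after Visit 5 on every table it affects.
- State in which table TEAEs with onset between Month 9 and Month 12 appear, so that the 12-month TEAE window and the table cut-off agree.

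The cost is SAP wording and table shells, with no change to data collection. Some related events with onset between Months 9 and 12 move to a separate table. Later triptorelin use on surveillance has to be identified from the concomitant medication data.
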